3.2 Rationale and Purpose

Study Rationale:

Falls are a common and significant problem among PLWH for various reasons.^{1,4–11} Antiretroviral therapy (ART) can control HIV viremia even in substance use-affected populations. But HIV-associated comorbidity and complications, in the context of possible premature aging —or more accurately—the earlier development of comorbidities in PLWH seen in older adults without HIV infection, now contribute to substantial impairment in people with HIV infection. These complications, including Frailty and impaired physical Function, can contribute to Falls and Fractures, and can be hastened by alcohol, illicit drug use, and polypharmacy (5+ medications). Fall prevention interventions developed for the elderly generally do not address alcohol, other drugs, or HIV medications, but would likely need to in order to be successful in PLWH. A focus on risks, including the interplay of common exposures (e.g. alcohol, illicit drugs, medications) and mediators (e.g. frailty), is therefore critical in order to develop tailored preventive interventions to reduce falls and related morbidity effective for PLWH.

Purpose:

This study is being conducted to assess the acceptability and feasibility of conducting a randomized trial of a 10-week virtual intervention aimed at reducing fall risk in PLWH who consume alcohol. This pilot trial will be used to inform feasibility of this study design prior to conducting a large-scale trial. To achieve this, we propose to recruit up to 50 participants from the Boston ARCH 4F Study, 40 of whom

will be randomized, to pilot test this fall prevention intervention. Further, we will assess the acceptability and feasibility of the intervention component by assessing number of virtual group intervention sessions attended and administering the Client Satisfaction Questionnaire (CSQ-8)¹⁴ at the conclusion of the intervention.

- 4 Objectives
 - 4.1 Study Objectives

The primary aim of the intervention is to assess acceptability and feasibility of a randomized trial of a 10week virtual fall prevention intervention.

- 4.2 Study Outcome Measures
- 4.2.1 Primary Outcome Measures

To assess intervention acceptability and feasibility, the primary outcomes include number of weekly intervention sessions attended (out of 10 sessions) and overall satisfaction with the intervention [assessed at study conclusion using the Client Satisfaction Questionnaire (CSQ-8)].¹⁴

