The BUMC OIT and BEDAC are physically located in the same building; all web and database servers used by BEDAC will be housed in a secure, professionally managed server room under the control of the BUMC OIT. Staff from BEDAC and BUMC OIT work to continually enhance their systems, procedures and processes to ensure compliance with industry and government standards for data security. All central systems are secured physically behind locked doors with access restricted to key personnel in the BUMC OIT. All databases will be backed up automatically on a nightly basis.

13. Statistical Plan

We will enroll up to n=50 participants to accommodate any situation in which an enrolled participant is not randomized to the intervention or control group. We aim to randomize up to n=40 participants

(approximately 20 randomized to the study intervention and approximately 20 randomized to the control group).

The goal of this pilot is to describe feasibility of the proposed trial and intervention and obtain preliminary estimates of falls related outcomes. This pilot is not intended to provide adequate statistical power for a formal comparison of the intervention and control groups on falls-related outcomes.

Confidence intervals for mean number of sessions attended, for those participants randomized to the intervention, will have a width of 0.44 standard deviations, and assuming approximately 80% of the approximately n=40 study participants complete follow-up, a confidence interval for the percent completing the study will have a width of 12 percentage points. While this pilot is not intended to test differences between the intervention and control groups, a t-test comparing means across groups (for example, on frailty scores) requires a large effect (corresponding to a Cohen's d of 1.0) to achieve 80% power, assuming 80% follow-up.

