To describe acceptance of the intervention among those randomized to intervention, mean and 95% confidence intervals will be provided for the number of sessions attended and overall satisfaction with the intervention. Compliance with the study protocol will be described the percent and 95% confidence of participants completing the study follow-up evaluation (of all participants). Estimates of intervention effects will be described through odds ratios and 95% confidence intervals for any falls during the intervention period, using logistic regression to control for baseline fall history. Mean differences and 95% confidence intervals for physical function score at the end of the study period, controlling for baseline physical function score, will be estimated through linear regression models.

14. Literature References

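### Section 13 reports two 95% confidence-interval half-widths as widths, so the stated precision for sessions attended and study completion looks about twice as good as the design gives

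*Combined protocol and SAP*

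**What the plan says.** Section 13 sets a target of 40 randomized participants, "approximately 20 randomized to the study intervention and approximately 20 randomized to the control group". It then describes the precision this provides. For mean sessions attended, the interval, "for those participants randomized to the intervention, will have a width of 0.44 standard deviations". For study completion, on the assumption that about 80% of about 40 participants are followed up, "a confidence interval for the percent completing the study will have a width of 12 percentage points".

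That sentence gives no confidence level, but the analysis paragraph that follows does. Among those randomized to the intervention, "mean and 95% confidence intervals will be provided for the number of sessions attended and overall satisfaction with the intervention". Compliance is to be described by "the percent and 95% confidence of participants completing the study follow-up evaluation (of all participants". Both intervals are therefore 95% intervals.

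Section 4.2.1 makes the number of sessions attended, out of 10, a primary outcome. Neither document section defines *width* as a half-width or margin of error, and neither figure carries a ± sign.

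**The concern.** The width of a confidence interval ordinarily means the upper limit minus the lower limit. For a mean of about 20 observations and a proportion based on about 40, a 95% interval as narrow as 0.44 SD or 12 points from end to end is not plausible. The values look like the distance from the estimate to one limit.

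Section 13 says the pilot is meant to describe feasibility and is not powered to compare the arms on falls-related outcomes. These two figures are therefore the plan's main numerical statement of what 40 participants can show about feasibility. If they are half-widths, someone judging in advance whether the pilot will be informative enough to plan retention in a larger trial would believe the precision to be twice as good as it is.

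**Working it through.** **Inputs, all from Section 13.** Intervention arm n = 20. Total n = 40. Completion p = 0.80. Confidence 95%, so z = 1.96.

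**Reproducing the plan's figures.**

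- Mean sessions attended, in SD units: z/√n = 1.96/√20 = 0.438. This rounds to the stated 0.44.
- Percent completing: z·√(p(1−p)/n) = 1.96 × √(0.16/40) = 1.96 × 0.0632 = 0.124, or 12.4 points. This rounds to the stated 12.

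Both formulas give the distance from the estimate to one limit, which is the half-width.

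**Full widths from the same inputs.**

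| Quantity | Stated as width | Half-width | Full width |
|---|---|---|---|
| Mean sessions, n = 20, normal quantile | 0.44 SD | 0.438 SD | 2 × 0.438 = 0.88 SD |
| Mean sessions, n = 20, t on 19 df | – | 0.468 SD | 0.94 SD |
| Percent completing, 80% of 40, normal approximation | 12 points | 12.4 points | 2 × 12.4 = 24.8 points |

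Read literally, a 12-point width around 80% is 74% to 86%. By the plan's apparent method the interval is 80% ± 12.4 points, or 67.6% to 92.4%.

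**Could another standard choice give the stated figures as full widths?**

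- *Other interval methods for the proportion (80% of 40, 95%):* full widths are 24.3 points (Wilson), 24.3 (Jeffreys), 24.8 (Agresti-Coull) and 26.6 (Clopper-Pearson). None is near 12.
- *Denominator of 50 (all enrolled):* 1.96 × √(0.16/50) = 11.1 points, full width 22.2.
- *Lower confidence level:* at 80% confidence the full widths are still 0.57 SD (n = 20) and 16.2 points (n = 40).
- *Confidence level that would be needed:* for the mean, z = 0.22 × √20 = 0.984, or about 67% confidence. For completion, z = 0.06/√(0.16/40) = 0.949, or about 66%.
- *Sample size that would be needed at 95%:* for the mean, (2 × 1.96/0.44)² = 79.4, so about 80 in the intervention arm. For completion, (2 × 1.96)² × 0.16/0.12² = 170.7, so about 171 participants.

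No standard variant reproduces either figure as a full width. Both reproduce directly as 95% half-widths.

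**The case against.** The strongest reply is that nothing was miscalculated. Both numbers are correct 95% margins of error, one word is used loosely in the same way twice, some authors do use *width* for the margin of error, and a statistician can recover the meaning from n in one line. In addition, nothing depends on the figures. Section 13 does not derive the 40 participants from them, the documents set no precision target or progression threshold, and the reported intervals will be computed from the data.

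Most of this stands. It is a labelling error, and it affects only the precision stated in advance. It does not make the text right, however. The plan nowhere signals the looser meaning, and under the ordinary meaning both figures are wrong by a factor of two. Readers who are not statisticians will not rework them.

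It is also fair to say that Section 13 names no interval method, so 0.88 SD and 24.8 points are not the only possible full widths. The choice of method moves them only to 0.94 SD for the mean and to between 24.3 and 26.6 points for completion, which leaves the conclusion unchanged.

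**Conclusion.** The concern holds. The two figures called widths in Section 13 are 95% half-widths. The full widths are about 0.88 SD for mean sessions attended (0.94 SD with a t interval) and about 25 points for percent completing, so the stated precision is too favourable by a factor of about 2.

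This rests on the plan's own inputs: about 20 in the intervention arm, 80% of about 40 completing, 95% confidence, and *width* read as the distance between the limits. The effect is confined to the precision stated in advance. The estimates, the reported intervals and the sample size are not affected. The neighbouring power statement does not share the fault: with 16 per arm after 80% follow-up, a t-test needs d = 1.02 for 80% power, in line with the 1.0 quoted.

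**What to change.** Relabel both figures in Section 13. Suggested text:

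> With about 20 intervention participants, the 95% CI for mean sessions attended will have a half-width of about 0.44 SD (full width about 0.88 SD; normal approximation). If 80% of 40 participants complete follow-up, the 95% CI for percent completing will be about ±12 percentage points (full width about 25 points, roughly 68% to 92%; normal approximation).

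If the mean will be reported with a t interval, which is the usual choice with an estimated SD and n = 20, give 0.47 SD and 0.94 SD instead. If the authors prefer not to commit to an interval method here, replacing *width* with *half-width* in both places is enough.

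The cost is one reworded sentence and a less favourable, but correct, statement of precision. No participants, procedures or analyses are added.

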3.1 Background Information

Up to a third of middle-aged people living with HIV infection (PLWH) experience falls each year.¹ Although not well-described in PLWH, falls are the most common cause of non-fatal injury in the US (8 million falls per year; 2.6 million treatment episodes; 750,000 hospitalizations, 22,000 deaths)^{2,3} and the cost in the elderly is enormous (\$20 billion/year), mostly from emergency department visits and hospitalizations (which have risen 50% in 7 years).² Falls are a common and significant problem in PLWH, and alcohol is a potent risk factor, increasing risk up to 17X.^{1,4–11} Alcohol, illicit drug use, and polypharmacy likely contribute to falls (e.g. from over-sedation and risk-taking behavior), risk factors for falls (e.g. frailty), and fall consequences (e.g. fracture, need for acute healthcare use). Interventions are needed to address falls in PLWH who use alcohol but none have been tailored for this population.

Efficacious interventions for the elderly exist^{12,13}; however, fall prevention interventions developed for the elderly generally do not address alcohol, other drugs, HIV medications, and HIV-associated comorbidity, but they would likely need to in order to be successful in PLWH. A focus on risks, including the interplay of common exposures (e.g. alcohol, illicit drugs, medications) and mediators (e.g. frailty), is therefore critical in order to develop tailored preventive interventions to reduce falls and related morbidity effective for PLWH.

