6.3 Analysis of Risks in Relation to Benefits

The principal risks of this study are loss of confidentiality and psychological stress. We will take an abundance of caution to protect the confidentiality of participants, and participants will be reminded of best practices prior to each weekly virtual group session. Participants will be provided various opportunities to discuss psychological distress with trained study staff and physician investigators. These risks are outweighed by the potential benefits that participants may receive from the intervention.

Participants who are assigned to the control arm may benefit from the provided educational materials.

Participants who are assigned to the intervention arm may benefit from weekly virtual group sessions and phone check-ins. These sessions will provide participants with the opportunity to discuss challenges

related to falls and alcohol use and ideas for overcoming these challenge. During preliminary qualitative research, Boston ARCH 4F participants expressed that group meetings and individual check-ins would be beneficial. Additionally, the home exercises may improve strength and balance in the participants. Furthermore, this intervention is tailored to address fall risk and alcohol use in this specific population, and it has the potential to reduce falls among PLWH who use alcohol more than a traditional fall prevention program.

The benefits outweigh the risks.

7 Study Subject Selection

- 7.1 Subject Inclusion Criteria
 - Male or female at least 18 years old
 - Prior or current participant in the Boston ARCH 4F Cohort
 - Any alcohol consumption in the last 30 days using Addiction Severity Index
 - Deemed a Fall Risk using the CDC STEADI Fall Risk Assessment Form¹⁹
 - Has reliable access to a phone or computer with internet connection

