7.2 Subject Exclusion Criteria

• Requires wheelchair for mobility

8 Study Procedures

8.1 Recruitment- Up to 50 participants will be recruited to the Fall Prevention Pilot study from the Boston ARCH 4F Study cohort. To identify potentially eligible participants, the Boston University Medical Campus (BUMC) Biostatistics and Epidemiology Data Analytics Center (BEDAC) will generate a list of potentially eligible participants from the Boston ARCH 4F cohort who previously (at prior Boston ARCH 4F Study cohort assessments) endorsed alcohol use and fall history based on responses to the Addiction Severity Index (ASI) and the AIDS Clinical Trials Group (ACTG) Fall History Questionnaire.^{20–22} Participants who have not provided their written informed consent to be contacted about other research studies will be excluded from this list. Research assistants (RAs) and the research coordinator (RC) approach participants on this list for phone screening.

8.2 Phone Screening of Eligibility -The RAs and RC will reach out to Boston ARCH 4F participants who have been identified as potentially eligible based on the criteria described above. Participants interested in the study, if they agree, will be screened over the phone by interview/questionnaire for eligibility. If the participant meets all inclusion criteria and does not meet any exclusion criteria, they will be offered participation in the Boston ARCH 4F Fall Prevention Intervention Pilot Study. All eligible participants will be informed about the study and their written consent will be sought.

8.3 Baseline Assessment - Enrolled participants will complete a baseline research interview (a series of questionnaires to assess fall history and efficacy, substance use, prescription medications, physical and social environment, food security, and frailty) and physical assessments (physical function measures

including grip strength, short physical performance battery, and vision acuity) in-person at BUMC with an RA or RC. Additionally, an occupational therapist member of the study team will conduct the Canadian Occupational Performance Measure to assess the participant's exercise-related skills, needs, and goals.

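### The odds ratio for any fall has no small-sample method: with 16 completers per arm, an arm without fallers occurs in 14% of trials (true OR 1) or 31% (true OR 0.5) at an assumed 15% 10-week risk, but in 2% or 9% at 25%

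*Combined protocol and SAP*

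**What the plan says.** The statistical analysis is in Section 13 (Statistical Plan). For falls it plans "odds ratios and 95% confidence intervals for any falls during the intervention period, using logistic regression to control for baseline fall history". It does not say how the interval is formed (Wald, profile likelihood or exact), and it gives no rule for an arm without fallers.

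The number analysed follows from the same section: about 20 randomized per arm, "assuming approximately 80% of the approximately n=40 study participants complete follow-up", hence about 16 completers per arm. One stated goal is to "obtain preliminary estimates of falls related outcomes". The section also says that the pilot is "not intended to provide adequate statistical power for a formal comparison" of the arms on falls-related outcomes.

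No 10-week fall risk appears anywhere. Section 3.1 says "Up to a third of middle-aged people living with HIV infection (PLWH) experience falls each year" and, of falls in this population, that "alcohol is a potent risk factor, increasing risk up to 17X". Section 7.1 requires drinking in the past 30 days and that the participant be "Deemed a Fall Risk using the CDC STEADI Fall Risk Assessment Form". Section 8.1 draws candidates from cohort members who had already reported alcohol use and falls. Section 4.2.2 lists falls as a secondary outcome and defines them broadly, so that losing balance and striking furniture counts.

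**The concern.** Ordinary logistic regression has no finite treatment odds ratio when an arm has no events. The likelihood keeps rising as the treatment coefficient goes to plus or minus infinity, whether or not baseline fall history is in the model. The fitted odds ratio is then 0 or infinite, and the Wald interval runs in effect from 0 to infinity. A profile-likelihood interval has one finite limit, but it tends to be too narrow. If neither arm has a faller, no odds ratio can be estimated.

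This odds ratio is the only between-arm estimate planned for falls themselves; physical function has its own model. If an arm is empty, the reported result would depend on a software default that the plan leaves open, or on a method picked after the data were seen.

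**Working it through.** **1. Completers per arm.** 0.80 × 20 = 16. The plan's own power statement supports this basis: with 16 per arm and d = 1.0, the normal approximation gives Φ(1.0 × √(16/2) − 1.96) = Φ(0.868) = 80.7%, as stated. The noncentral t gives 78.1%. Two-sided 5% is assumed.

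**2. The only fall rate in the documents.** One third per year at a constant hazard gives 1 − (2/3)^(10/52) = 7.5% over 10 weeks. It describes middle-aged people with HIV generally, not the people enrolled here, so the control risk p0 is varied as an assumption. The hazard multiple needed to reach p0 is ln(1 − p0) / [ln(2/3) × 10/52].

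**3. Chance of an empty arm.** With n per arm:

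- at least one arm empty: 1 − [1 − (1 − p0)^n] × [1 − (1 − p1)^n]
- both arms empty: (1 − p0)^n × (1 − p1)^n
- p1 = p0 for a true odds ratio of 1; for 0.5, p1 = o/(1 + o) with o = 0.5 × p0/(1 − p0)

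At p0 = 15%, 0.85^16 = 0.074, so with no effect the chance is 1 − (1 − 0.074)² = 14.3%. With an odds ratio of 0.5, p1 = 8.1% and (1 − p1)^16 = 0.258, giving 1 − 0.926 × 0.742 = 31%.

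| Assumed control risk | Multiple of general hazard | At least one arm empty, OR 1 / OR 0.5 | Both empty, OR 1 / OR 0.5 |
|---|---|---|---|
| 7.5% | 1.0 | 49% / 66% | 8% / 15% |
| 15% | 2.1 | 14% / 31% | 0.5% / 1.9% |
| 20% | 2.9 | 6% / 18% | 0.1% / 0.4% |
| 25% | 3.7 | 2% / 9% | at most 0.1% |
| 35% | 5.5 | 0.2% / 2.3% | below 0.1% |

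If all 40 are followed (n = 20), the chance of at least one empty arm is 38%/57% at 7.5%, 8%/22% at 15% and 0.6%/5% at 25%.

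**4. What the interval type does: 0/16 v 3/16 fallers.** Fisher's p = 0.23. Unadjusted, the likelihood-ratio statistic against OR 1 is 2 × [(3 ln 0.1875 + 13 ln 0.8125) − (3 ln 0.09375 + 29 ln 0.90625)] = 2 × (−7.72 + 9.96) = 4.47. This is above 3.84, so the profile interval excludes 1. The Firth-penalised statistic is 2.83, so its interval includes 1.

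Adjusting for a yes/no fall history, with 11 of 16 per arm positive (an assumption; the plan does not say how history is coded), the maximum-likelihood profile upper limit is 0.54 to 0.80, depending on which controls fell. Firth gives an odds ratio of 0.07 to 0.12 with an upper limit of 1.10 to 1.40 and a lower limit below 0.001. The risk difference is −19 points (Newcombe −43 to +4).

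**5. How often each 95% interval wrongly excludes 1.** All 17 × 17 outcomes were enumerated, unadjusted, 16 per arm, true OR 1:

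| Risk | ML profile | Firth profile |
|---|---|---|
| 7.5% | 6.6% | 1.6% |
| 15% | 7.8% | 4.2% |
| 25% | 6.2% | 4.3% |

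**6. Shrinkage.** In 3,000 simulated trials per scenario with a true odds ratio of 0.50, the geometric mean of the Firth estimate was about 0.60 at 7.5% risk (0.65 if trials with no faller at all count as 1), 0.53 to 0.54 at 15%, and 0.49 to 0.51 at 25% to 35%. Maximum likelihood, kept only when finite, gave roughly 0.8 at 7.5%, 0.63 to 0.66 at 15%, 0.50 to 0.52 at 25% and 0.47 to 0.48 at 35%. The fall-history prevalence (0.7 or 0.9) and its odds ratio (2) are assumptions, and simulation error is a few hundredths.

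**The case against.** The strongest defence is that little depends on this number. Falls are secondary, the comparison is openly unpowered and descriptive, no go/no-go rule uses it, and an empty arm would be obvious to anyone reading the counts. That stands, and it keeps the point minor. It does not remove it: the issue is whether a planned estimate can be reported at all, which is separate from power.

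Second, the participants are selected for fall risk, earlier falls and drinking, under a wide definition of a fall. This also stands. A reader might infer from the 7.5% row that the planned fit will more likely than not fail. The documents do not support that, because the rate belongs to a different population. They do not settle a higher risk either: the 17-fold figure for alcohol is an upper bound without a dose and cannot be used to choose a row.

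Third, a reader might infer that profile intervals would manufacture a benefit. The excess is modest: 6% to 8% false exclusion against a nominal 5%. The 0 v 3 split, in either direction, arises in only 4.9%, 3.4% and 0.4% of trials at 7.5%, 15% and 25% risk with no effect. Nor is Firth immune: at 0/16 v 4/16 its unadjusted statistic is 4.23, so it excludes 1 although Fisher's p = 0.10.

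Fourth, a one-line fallback for empty arms might seem enough. It would be better than silence. However, keeping maximum likelihood whenever it is finite selects the trials with fallers in both arms. When events are few, that pulls the average further toward 1 than Firth does (step 6 of the working). At 25% risk or more the choice hardly matters.

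Last, Section 12.1 says that the data center keeps analytic plans. These are not in the documents and may cover the point, so the claim is only that Section 13 is silent.

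**Conclusion.** The gap is real, and the point is a minor, cheap improvement. As written, the method returns no usable odds ratio when an arm has no fallers. Whether that is a frequent or a negligible event turns on a 10-week risk that the documents do not give: it is a material possibility around 15% and close to irrelevant at 35%. The higher chance at each risk also requires a true odds ratio of 0.5; it is not the upper end of an uncertainty range. The empty-arm probabilities are exact given 16 completers per arm and independent participants. The adjusted example and the simulated averages rest on the fall-history assumptions labelled above. Nothing here bears on session attendance, satisfaction or the completion percentage.

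**What to change.** In Section 13, before outcome data are seen:

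- Estimate the odds ratio for any fall by Firth-penalised logistic regression with the same treatment and baseline fall-history terms, and with profile-penalised-likelihood 95% intervals.
- Always report the number and percentage of fallers per arm and the unadjusted risk difference with a Newcombe 95% interval.
- If neither arm has a faller, report only the counts and the risk-difference interval (for 0/16 v 0/16, −19 to +19 points), with no odds ratio.
- State how baseline fall history is coded.

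The cost is a few sentences and a standard software option, with no extra participants or data. The price is some shrinkage toward 1 and very wide intervals when events are few. An interval that just excludes 1 should still be read against the counts.
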